5.2.1. Analyses for Binary Endpoints

Binary data will be summarized by number of unique participant incidence and proportion in the analysis set. A 2-sided 95% CI using Clopper-Pearson exact method will be provided if the sample size per cohort permits.

5.2.2. Analyses for Continuous Endpoints

Continuous data will be summarized with the mean, median, minimum, maximum, coefficient of variation, standard deviation, and 2-sided 95% CIs if the sample size permits.

5.2.3. Analyses for Categorical Endpoints

Categorical data will be summarized by number of unique participant incidence and proportion of participants in each category. A 2-sided 95% CI of the proportion if the sample size permits and deemed necessary.

5.2.4. Analyses for Time-to-Event Endpoints

The time-to-event data will be presented for individual participant, by dose level cohort in Part 1, expansion cohort in Part 2, and overall, when applicable. Time-to-event endpoints will be summarized using the Kaplan-Meier method and estimated survival curves will be displayed graphically when appropriate. Graphs will describe the number of participants at risk over time and the number censored. The median, quartiles, and probabilities of an event at particular points in time will be estimated by the Kaplan-Meier method, when possible based on the number of observed events. Confidence

intervals for medians and quantiles, based on the Brockmeyer-Crowley method, may be presented (Brockmeyer and Crowley, 1982). Confidence intervals for the estimated probability of an event at a particular time point may be generated using the Greenwood formula.

Time to event endpoints include OS, PFS, DOR, and TTP.

5.3. Methods to Manage Missing Data

For the analysis of safety endpoints, the sponsor data standard rules for imputation will be applied. See CDISC and PDS Safety Rulebooks for details.

5.3.1. Missing Dates

In compliance with Pfizer standards, if the day of the month is missing for any date used in a calculation, the 1st of the month will be used to replace the missing date unless the calculation results in a negative time duration (e.g., date of onset cannot be prior to day one date). In this case, the date resulting in 0 time duration will be used. Pfizer standards are also used if both month and day are missing (Jan 1 unless negative time duration). This excludes the pharmacokinetic and ECG analyses, which will only use the actual date collected or if date not available deem the data missing.

5.3.2. Efficacy Analysis

[figure not shown]
No imputation will be performed for tumor assessments that will be used for the binary efficacy endpoints. Every effort will be made to retrieve data in the CRF, however missing data will be left as is. The reasons for missing tumor assessments will be collected.

For the time-to-event endpoints, the missing data handling method will be censoring. Censoring rules for time-to-event endpoints are detailed in [Appendix 1](#).

A horizontal bar chart comparing the percentage of countries with CCI and CCI+ across different regions. The y-axis lists regions: Central America, South America, Latin America, Central America and South America, and Global. The x-axis represents the percentage of countries, ranging from 0% to 100%. The legend indicates that dark blue bars represent CCI and light blue bars represent CCI+.

Region	CCI (%)	CCI+ (%)
Central America	~10	~10
South America	~30	~30
Latin America	~95	~95
Central America and South America	~70	~70
Global	~60	~60

CCI

5.3.6. QTc

For the collected QT (QTc) analyses, no values will be imputed for missing data.

Further details are given in Section [6.9.4](#).

5.4. Statistical Considerations of COVID-19 Impacted Data

In March 2020, the World Health Organization (WHO) announced a global pandemic of the virus SARS-CoV-2 and the resulting disease COVID-19. During the conduct of this trial, if any participant's data is impacted by this pandemic, the following considerations will be given in the data analyses:

- a) If a participant dropped out of the study during the DLT evaluation window in Part 1 due to COVID-19, a replacement participant may be added.
- b) Death caused by COVID-19 is still considered as an "event" in the analysis of PFS and OS. If deemed necessary, a sensitivity analysis may be performed where COVID-19 driven death is censored at the death date.
- c) If a scheduled tumor radiographic scan is delayed out of the Schedule of Activity allowable window, or is missing (i.e. participant skipped a scheduled tumor radiographic scan) due to any reasons related to the pandemic, this delay or

missingness does not alter the censoring rules for PFS or TTP as described in Appendix 1. A censoring reason of “COVID-19” may be added to the PFS or TTP summary if the specific reason of tumor scan delay or missing can be attributed to COVID-19. If deemed necessary, a sensitivity analysis may be performed where participants would be censored at the date of their last scan prior to their COVID-19 diagnosis.

In the confirmed ORR analysis, as described in Section 6.2.3, if a response can't be confirmed by a subsequent tumor scan because of the pandemic (i.e., the subsequent tumor scan wasn't performed), then the initial response will be considered as unconfirmed. No sensitivity analysis will be performed.

- d) Any COVID-19 related symptoms are to be captured as adverse events in the case report form. Those adverse events will be summarized in the same manner as other adverse events. If a label of COVID-19 can be identified in the investigator provided adverse event term, then a separate AE listing may be provided for just the COVID-19 related events.
- e) If identifiable, the COVID-19 related data points, including missing data where the reason of missing is identified as COVID-19 related (site closure hence data could not be captured; participants skipped a visit because of concern over the pandemic), protocol deviations driven by COVID-19, safety events caused by COVID-19 may be separately listed.

6. ANALYSES AND SUMMARIES

6.1. Primary Endpoints for Part 1

6.1.1. Dose-Limiting Toxicities (DLTs)

- Analysis set: Per protocol analysis set
- Analysis methodology:

For the purpose of dose escalation, the DLT observation period/window will be the first cycle (defined as 28 days after the start of study treatment), for each participant. Whether an adverse event a participant experienced during the DLT window is determined as a DLT or not is based on the DLT definitions provided in Section 4.3.3 of the protocol.

The DLT events will be summarized by dose level. A listing of the DLT events will also be provided in which the participant's primary diagnosis (malignancy), dose level the participant was enrolled to, DLT event start day and stop day relative to the C1D1 dose date, the DLT event term, NCI CTCAE grade, relatedness to the investigational product (PF-07209960), outcome of the event, along with other variables deemed important, will be included.

- Missing data: All enrolled participants in Part 1 should have an indicator variable derived to be either 1 (yes) or 0 (no) based on the DLT definitions (provided in

Section 4.3.3 of the protocol) and participant's safety data during the DLT observation window. If a participant fails to have a value on the indicator variable because the participant being non-DLT-evaluable, the participant may be replaced.

6.1.2. Adverse Events (AEs)

- Analysis set: Safety analysis set
- Analysis methodology:

AEs will be characterized by type, frequency, severity (as graded by NCI CTCAE version 5.0, except CRS, which will be graded by ASTCT criteria (Lee et al., 2019)) timing, seriousness, and relationship to study therapy. Further description is given in Section 6.9.1. The primary focus will be on TEAEs. TEAEs is defined as any AE that occurs during the on-treatment period, defined in Section 3.5. AEs that occur after the on-treatment period may still be recorded in the clinical database and will be included in the AE listings, but will not be included in the on-treatment emergent AE summaries.

See Section 6.9.1 for details on the specific AE summaries to be provided.

- Missing data: If an AE start or stop date is missing, imputation will be performed according to Section 5.3.1. The imputed dates will be used to determine whether the AE is to be included in the TEAE summary. The missing AE start or stop dates will be listed as is in AE listings. When the CTCAE grade is missing for an AE, the AE will be excluded from the CTCAE grade summary table.

6.1.3. Laboratory abnormalities

- Analysis set: Safety analysis set
- Analysis methodology:

Laboratory abnormalities will be presented as tables and characterized by type, frequency, severity (as graded by NCI CTCAE version 5.0), and timing. For laboratory tests without CTCAE grade definitions, results will be categorized as normal, abnormal high/low, or not done. The number and percentage of participants who experienced laboratory test abnormalities will be summarized according to worst toxicity grade observed for each laboratory assay. Shift tables of baseline grade to worst post-baseline grade will be provided. Quantitative summaries for change from baseline and percent change from baseline for the laboratory tests may be provided, if deemed necessary. These summaries will be presented for the entire on-treatment period and for the various subgroups of the study (by dose level for Part 1 and by expansion cohort for Part 2).

Hematology, serology and coagulation lab results can be combined into one summary output. Separate summaries will be created for chemistiy tests. Urinalysis and pregnancy tests will not be summarized and will only be listed.

- Missing data: Missing lab values will not be imputed.

6.2. Secondary Endpoints for Part 1

CCI

6.2.2. Immunogenicity

- Analysis set: Immunogenicity set
- Analysis methodology:

For the immunogenicity data, the percentage of participants with positive ADA and NAb each will be summarized. Listings and summary tabulations of the ADA and NAb data at baseline and post-randomization will be generated. For participants with positive ADA or NAb, the magnitude (titer), time of onset, and duration of ADA or NAb response will also be described, if data permit. The potential impact of immunogenicity on PK and clinical response including pharmacodynamic markers, safety/tolerability and efficacy will be explored, if warranted by the data.

6.2.3. Tumor Response

- Analysis set: Response evaluable set

- Analysis methodology:
 - For treatment response, 'start date' is defined as the first date that a participant received the study intervention.
 - Overall Response Rate (ORR)
 - ORR as assessed using RECIST version 1.1. ORR is defined as the proportion of participants who achieved CR or PR per RECIST version 1.1 (details are provided in the protocol, Section 8.1.1 and Appendix). Both confirmed ORR and uORR will be determined based on the confirmed and unconfirmed CR and PR, definitions provided below.
 - Disease Control Rate (DCR)
 - A participant with a BOR of CR, PR, non-CR/non-PD or SD is defined as having DC. The DC rate is defined as the percentage of participants with DC in the specified analysis set.
 - Best Overall Response (BOR)
 - **Complete Response (CR):** Two objective assessments of CR a minimum of 4 weeks apart documented before PD.
 - **Partial Response (PR):** Two objective statuses of PR or better (PR followed by PR or PR followed by CR) a minimum of 4 weeks apart documented before PD, but not qualifying as CR. Sequences of PR- Stable- PR are considered PRs as long as the two PR responses are observed at a minimum of 4 weeks apart.
 - **Stable Disease (SD)** (applicable only to participants with measurable disease at baseline): At least one objective status of stable disease or better documented at least 6 weeks after 'start date' and before PD but not qualifying as CR or PR.
 - **Non-CR/non-PD** (applicable only to participants with non-measurable disease at baseline): at least one non-CR/non-PD assessment (or better) documented at least 6 weeks after 'start date' and before first documentation of PD (and not qualifying for CR or PR).
 - **Progressive Disease (PD):** Progression documented within 16 weeks after 'start date' and not qualifying as CR, PR or SD.
 - **Not Evaluable (NE):** All other cases. Note that reasons for NE should be summarized and the following reasons could be used:
 - No adequate baseline assessment (defined below).

- No evidence of disease at baseline.
- No post-baseline assessments due to early death, i.e., death prior to 8 weeks after ‘start date’.
- No post-baseline assessments due to other reasons (adequate post-baseline assessments defined below).
- All post-baseline assessments have overall response NE.
- New anti-cancer therapy started before first post-baseline assessment.
- SD of insufficient duration (<6 weeks after ‘start date’ without further evaluable tumor assessments).
- PD too late (>16 weeks after ‘start date’).
- Special and rare cases where BOR is NE due to both SD of insufficient duration (‘too early’) and late PD will be classified as ‘SD of insufficient duration’.
- uCR is defined as one objective status of CR documented before PD.
- uPR is defined as one objective status of PR documented before PD but not qualifying as uCR.

Note: An objective status of PR, SD, or Non-CR/Non-PD cannot follow one of CR. SD can follow PR only in the rare case that tumor increases by less than 20% from the nadir, but enough that a previously documented 30% decrease from baseline no longer holds. If this occurs the sequence PR – SD – PR is considered a confirmed PR. A sequence of PR – SD – SD – PD would be a best response of SD if the window for SD definition has been met.

- Tumor response will be presented in the form of participants data listings that include, but are not limited to: tumor type, initial actual dose received, tumor response at each assessment, and best overall response. Progression date, death date, date of first response, last assessment date, and date of last contact will also be listed. Additionally, a graphical representation (swimmer plot) will be provided to display tumor response overtime and a waterfall plot displaying the best percentage change in tumor size will be provided.
- Definition of adequate assessments
 - Baseline: The following conditions must be met for a baseline assessment to be adequate,

- Assessment of all lesions (target, and non-target) must be within 28 days prior to and including the ‘start date’.
- All lesions (target and non-target) must have non-missing assessments.
- Baseline lesions must be assessed with an acceptable method of tumor assessment as specified in the protocol and could include contrast and non-contrast MRI, contrast and non-contrast CT, and X-ray.
- Post-baseline: An adequate post-baseline assessment is defined as an assessment where a response of CR, PR, SD, non-CR/non-PD, or PD can be determined.
- Missing data: Missing data will not be imputed.

[figure not shown]
6.2.4. Time-to-event and duration endpoints

- Analysis set: Response evaluable set
- For treatment response, unless noted otherwise ‘start date’ is defined as the first date that a participant received the study intervention.
- Duration of Response (DOR)
 - Duration of response is defined as the time from start date (which is the date of first documentation of PR or CR) to date of first documentation of objective progression, death due to any cause, or time of censoring. Both confirmed DOR and uDOR will be determined separately for the subset of participants with a confirmed and unconfirmed objective response of CR or PR (defined above in Section 6.2.3). The outcome, event dates and reasons for censoring for DOR will match those used for the analysis of PFS. However, participants will not be censored for inadequate baseline assessment or for no adequate post-baseline assessment, as only participants with an objective response are included in this analysis of DOR. Censoring and event rules are further outlined in [Table 3](#).
- Progression Free Survival (PFS)
 - PFS is the time from ‘start date’ to date of first documentation of PD, death due to any cause, or censoring, whichever occurs first. Exceptions to using a PD or death date are outlined in [Table 3](#).
- Time to Progression (TTP)
 - TTP is the time from ‘start date’ to the date of the first documentation of PD or censoring. TTP is similar to PFS except that death is not treated as an event and is censored. TTP censoring rules are outlined in [Table 4](#).

- Missing data: Missing data will be handled by censoring rnlle. Time points where the response is NE, or no assessment was performed will not be used for determining the censoring date.

6.3. Exploratory Endpoints for Part 1

CCI

6.4. Primary Endpoints for Part 2

6.4.1. Adverse Events (AEs)

AEs in Part 2 will be summarized in the same fashion as Part 1, which is described in Section 6.1.2.

6.4.2. Laboratory abnormalities

Laboratory abnormalities in Part 2 will be summarized in the same fashion as Part 1, which is described in Section 6.1.3.

6.4.3. Overall Response Rate (ORR)

ORR will be determined and summarized in Part 2 in the same fashion as Part 1, which is detailed in Section 6.2.3.

6.5. Secondary Endpoints for Part 2

6.5.1. Pharmacokinetic Analysis

Pharmacokinetic analysis for Part 2 will follow what was done for Part 1, which is detailed in Section 6.2.1.

6.5.2. Immunogenicity

Immunogenicity will be determined and summarized in Part 2 in the same fashion as Part 1, which is detailed in Section 6.2.2.

CCI

I [REDACTED]

[REDACTED]

I [REDACTED]

[REDACTED]

6.5.4. Tumor Response

DCR, DOR, PFS, and TTP will be determined and summarized in Part 2 in the same fashion as Part 1, which is detailed in Section [6.2.3](#).

6.5.5. Overall Survival

OS will be determined and summarized in Part 2 in the same fashion as Part 1, which is detailed in Section [6.2.3](#).

6.6. Exploratory Endpoints for Part 2

CCI

[REDACTED]

6.7. Subset Analyses

There are no planned subset analyses.

6.8. Baseline and Other Summaries and Analyses

6.8.1. Baseline Summaries

Baseline characteristics such as demographics, prior medication, and primary diagnosis will be tabulated and listed. The Safety Analysis Set will be used.

6.8.2. Analysis Sets

Participant inclusion into the analysis sets in [Table 2](#) will be tabulated. A listing will be also be provided for the analysis sets.

6.8.3. Anti-Cancer Therapies

Prior anti-cancer therapies (drug therapy, radiation, and surgery) will be tabulated. Similarly, follow-up anti-cancer therapies (drug therapy, radiation, and surgery) will also be tabulated.

6.8.4. Study Conduct and Participant Disposition

Participant discontinuation from treatment and study will be tabulated and listed for each participant separately with their reason for discontinuation. The Safety Analysis Set will be used. Similarly, potentially important protocol deviations will be tabulated and listed for each participant. Participant disposition at baseline, end of treatment, and at long-term follow-up will be tabulated. Participant disposition will be listed for all phases of the trial.

6.8.5. Study Treatment Exposure

The Safety Analysis Set will be used.

The following will be summarized by treatment dose level and overall, for Part 1 and by expansion cohort for Part 2:

- Number of participants;
- Duration of Treatment (DOT): DOT is defined as the last active dose date minus the first active dose date + 1. DOT will be summarized, as a continuous variable and summary statistics including the mean, median, standard deviation and range will be provided. In addition, a DOT will be summarized as a categorical variable in 3 month intervals, e.g., the frequency of participants with a DOT of 3 months, 6 months, 9 months, etc.;
- Dose modifications are described in the protocol. Dose modifications to study intervention due to AEs include the following (ideally presented in one table):
 - Number (%) of dose interruptions (include both known and unknown dates). Dose interruptions is defined as a planned dosing day with 0 mg total dose administered;
 - Number (%) of dose interruptions related to AEs, defined as “Was the Actual Dose adjusted from planned?” = “ADVERSE EVENT(S)” and “Latest Action Taken with Study Treatment:” = “DRUG INTERRUPTED”;
 - Number (%) of participants with dose reductions. A dose reduction is defined as a day when the actual dose is less than the planned dose at enrollment and the actual dose is greater than 0 mg (i.e., missed doses are not counted as a reduction);
 - Number (%) of dose reductions related to AEs, defined as “Was the Actual Dose adjusted from planned?” = “ADVERSE EVENT(S)” and “Latest Action Taken with Study Treatment:” = “DOSE REDUCED”;
 - Number (%) of participants with a dose increase. A dose increase is defined as a day when the actual dose is greater than the planned dose;

- Number (%) of participants with dose reductions or interruptions for each reason (AE vs insufficient clinical response vs Other);

The following will be summarized for cumulative dose by dose level in Part 1 and expansion cohort in Part 2:

- Summary statistics (mean, median, standard deviation and range) of cumulative dose and cumulative percent of administered dose (compared to planned dose);
- Actual dose intensity (mg/day): Defined as cumulative actual dose received (mg) divided by the number of doses scheduled per protocol during treatment period;
- Ratio of actual dose intensity to planned dose intensity. Where planned dose intensity is defined as a participant's planned starting dose.

Listings by participant (ordered by dose level): start date and stop date of dosing period within each cycle (including records with 0 mg), total daily dose received for each dosing period, any missed doses with unknown dates (yes/no), number of missed doses with unknown dates, reason for any dosing changes, and cycle number relative to the dosing period.

Listings by participant and cycle (ordered by dose level): cycle length, total planned dose, total actual dose received, percentage of planned dose, dose reduction (yes/no), and dose interruption (yes/no).

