6.1.1. Administration

PF-07209960 will be administered once every 2 weeks as a flat dose SC injection or IV infusion over 1 hour (± 10 minutes).

Each participant may receive PF-07209960 until disease progression, unacceptable toxicity, withdrawal of consent, or study termination. Treatment beyond disease progression may be discussed with sponsor if the investigator assesses that it is the participant's best interest to continue with treatment and would not derive as much benefit from alternative therapy and has met the criteria for treatment beyond progression as outlined in [Section 4](#) .

Subcutaneous administration

Qualified and trained investigator site personnel will administer PF-07209960 to participants by SC injection. Ideally, each injection may be up to 2 mLs in volume. However, if the maximum volume allowed per institution's policy is lower, the number of injections may

increase to accommodate this difference in volume to ensure the correct final dose is delivered.

Study drug should be administered to the abdomen (with preference given to the lower quadrants when possible). Refer to [Appendix 12](#), for details on administration of multiple injections to the abdomen. Study staff should refer to the IP Manual for specific instructions on the handling and preparation of study drug.

Cycle duration: A cycle is defined as 28 days, regardless of missed doses or dose delays.

Intravenous administration

Based on the available emerging clinical data (including safety/tolerability, PK, PD) from the dose escalation cohorts with SC Q2W administration, IV infusion Q2W administration may be explored in successive dose cohorts. If IV administration is introduced, PF-07209960 will be administered over 1 hour (± 10 minutes) time period without adjustment for body size at every cycle as indicated in the IP manual.

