6.6.2. Dose Delays

Re-treatment following treatment interruption for treatment-related toxicity may not occur until all of the following parameters have been met:

- ANC $\geq 1,000/\text{mm}^3$.
- Platelet count $\geq 50,000/\text{mm}^3$
- Nonhematologic toxicities have returned to baseline or Grade ≤ 1 severity (or, at the investigator's discretion, Grade ≤ 2 if not considered a safety risk for the participant).

If a treatment delay results from worsening of hematologic or biochemical parameters, the frequency of relevant blood tests should be increased as clinically indicated.

If these conditions are met within 4 weeks of treatment interruption, PF-07209960 may be resumed. Refer to the Section 6.6.3 for AEs requiring dose reduction at the time of treatment resumption.

If participants require discontinuation of PF-07209960 for more than 4 weeks from last dose (2 missed dose) at any time during the study, then study treatment should be permanently discontinued, unless the investigator's benefit/risk assessment suggests otherwise after discussion with the sponsor's medical monitor.

If a treatment interruption continues beyond Day 28 of the current cycle, then the day when treatment is restarted will be counted as Day 1 of the next cycle.

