2.2. Study Design

This is a Phase 1, open label, multicenter, multiple dose, dose escalation, safety, PK and PD study of PF-07209960 in participants with selected locally advanced or metastatic solid tumors (anti-PD-I/PD-LI resistant NSCLC, SCCHN, RCC, UC; or anti-PD I naive OvCa and MSS CRC for whom no standard therapy is available, or would not be an appropriate option in the opinion of the participant and their treating physician, or participants who have refused standard therapy.

The study contains 2 parts, single agent dose escalation (Part 1) followed by a dose expansion at the RP2D (Part 2). The overall study design is depicted in the schema (Section 1.2 in the protocol). Successive cohorts of participants in Part 1 will receive escalating doses of PF-07209960 as SC or IV administration every 2 weeks. The first and second participant in each dose level must be enrolled >72 hours apart. BLRM guided by EWOC principle will be used to guide dose escalation process and determine the MTD/IRP2D. Part 1 will estimate the MTD/IRP2D in sequential dose escalation cohorts for PF-07209960 as single agent in participants with selected solid tumors. After the MTD/IRP2D for PF-07209960 single agent is determined, Part 2 expansion will be initiated in participants with selected solid tumors as informed by Part 1.

Number of Participants: *The total number of participants enrolled to study intervention is estimated to range from approximately 74 to 172. Approximately 14-22 participants are expected to be enrolled in Part 1 dose escalation. Each cohort in Part 2 will enroll 20-30 participants. Approximately 60-90 participants will be initially enrolled in the first three cohorts, with the option to further enroll approximately 40-60 participants in an additional two cohorts.*

Intervention Groups and Duration: *PF-07209960 will be administered as monotherapy, SC or IV infusion over 1 hour (± 10 minutes) on Days 1 and 15 in 28 day cycles as described in Section 4.3.1 in the protocol. Treatment with study intervention will continue until either disease progression, unacceptable toxicity, participant refusal, or whichever is earliest, unless the investigator and medical monitor agree to treatment beyond disease progression based on individual benefit/risk assessments or agree to discontinue treatment or the study is terminated.*

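### Treatment duration credits the last two-weekly dose with 1 day, 13 days short per participant; separately, dose intensity divides by doses in an undefined treatment period

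*SAP*

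**What the plan says.** **Schedule.** SAP 2.2 gives the drug "on Days 1 and 15 in 28 day cycles", and Protocol 6.1.1 confirms dosing once every 2 weeks. Protocol 6.1.1 also fixes the cycle: "A cycle is defined as 28 days, regardless of missed doses or dose delays".

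**Duration.** SAP 6.8.5 states "DOT is defined as the last active dose date minus the first active dose date + 1". It is reported as a continuous variable, and in addition "DOT will be summarized as a categorical variable in 3 month intervals". No day count is given for a month.

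**Dose intensity.** SAP 6.8.5 labels actual dose intensity mg/day and computes it as "cumulative actual dose received (mg) divided by the number of doses scheduled per protocol during treatment period". Planned dose intensity is the participant's planned starting dose, and the ratio of the two is summarized. The section does not say when the treatment period ends. The nearest definition is the safety on-treatment period in SAP 3.5. It ends at last dose + 28 days (or + 90 days in the extended version), or the day before new anti-cancer therapy if earlier.

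**Withheld doses.** SAP 6.8.5 counts a planned dosing day with nothing given as an interruption, and its listings keep 0 mg records. Protocol 6.6.2 directs permanent discontinuation once the gap since the last dose exceeds 4 weeks, which it equates to 2 missed doses, unless a benefit/risk assessment discussed with the medical monitor suggests otherwise.

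**The concern.** Subtracting dates and adding 1 counts the last dose as one day of treatment. That fits a drug taken daily. Here each dose opens a 14-day interval, so a participant who completes the 28-day first cycle, which is also the DLT window, is reported as treated for 15 days, and one who received a single dose for 1 day. The proportional understatement is greatest in those with the least exposure.

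Nearby text suggests that the exposure section was not adapted to this schedule. Dose intensity carries a per-day unit, the listings in SAP 6.8.5 refer to a total daily dose, and SAP Table 2 asks for at least 11 doses in each of the first two cycles, although only 2 per cycle are planned. This is an inference; the SAP does not say where the wording came from.

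Dose intensity has its own problem. Its denominator depends on a period with no stated end, so the same dosing record can yield different ratios. That matters most for a participant whose doses are withheld and who then stops for good, a case that Protocol 6.6.2 foresees. DOT and dose intensity are presented by dose level in Part 1, where readers will look at whether a dose can be delivered over time.

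**Working it through.** The documents report no DOT or dose-intensity value, so there is nothing to reproduce. The check is date arithmetic.

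**1. Duration.** Inputs: dosing every 14 days (SAP 2.2, Protocol 6.1.1) and the SAP 6.8.5 rule. With k doses on schedule, dose k falls on Day 1 + 14(k − 1).

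- SAP rule: 14(k − 1) + 1
- Last dose credited with its full interval: 14(k − 1) + 14 = 14k
- Difference: 13 days for any k

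| Doses | SAP DOT (days) | 14k (days) | Shortfall |
|---|---|---|---|
| 1 | 1 | 14 | 93% |
| 2 | 15 | 28 | 46% |
| 4 | 43 | 56 | 23% |
| 7 | 85 | 98 | 13% |
| 12 | 155 | 168 | 8% |

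If 3 months is taken as about 91 days (an assumption), the seven-dose participant falls below the cut under the SAP rule and above it when the last interval counts. With 6 doses (71 v 84) or 8 doses (99 v 112) the first cut is not crossed.

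**2. Dose intensity.** At an unreduced dose, the ratio of actual to planned dose intensity is doses given ÷ doses scheduled. Assume planned days run every 14 days from first dose, including through a hold. Let g doses be given and 2 then withheld before a permanent stop. The withheld doses were due 14 and 28 days after the last dose.

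| End of treatment period | Scheduled doses | g = 2 | g = 4 | g = 6 |
|---|---|---|---|---|
| Last active dose | g | 100% | 100% | 100% |
| Through the withheld doses, or last dose + 28 days | g + 2 | 50% | 67% | 75% |
| Last dose + 90 days | g + 6 | 25% | 40% | 50% |

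The + 90 row adds planned days at + 14, 28, 42, 56, 70 and 84. The + 28 and + 90 rows assume no new anti-cancer therapy before those days.

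**3. Are the two linked?** Dose intensity is not computed from DOT. If the period ended 13 days after the last dose, to match a + 14 rule for DOT, the next planned dose (day + 14) would still lie outside it and the ratio would stay at 100%. Doses withheld mid-course and then resumed stay in the denominator even when the period ends at the last active dose: 2 given, 2 withheld, 1 given is 3/5 = 60%.

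**4. Unit.** Two doses of 1 unit in a 28-day cycle give 2/2 = 1 unit per scheduled dose, which is what the formula returns. Per day it would be 2/28 = 0.07. The mg/day label does not match the formula, whereas the planned value (a starting dose) is per dose.

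**The case against.** The strongest reply is that first-to-last dose plus one day is an open, reproducible convention. The shortfall is the same 13 days for each participant, so absolute differences between dose levels are largely untouched, and the large percentages come from dividing a constant by a short duration. That is fair, but the constant does not cancel in the 3-month categories. A completed 28-day cycle reported as 15 days also misdescribes exposure.

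Several stronger conclusions are tempting, and the documents do not support them.

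- *The DOT formula removes withheld doses from dose intensity.* It does not; the two calculations are separate.
- *Participants who stop after a toxicity hold score 100%.* Only if the period ends at the last active dose, which the SAP does not state. Under the 28-day period in SAP 3.5 the two withheld doses count.
- *A poorly tolerated dose would therefore look deliverable.* Interruption counts and 0 mg listings (SAP 6.8.5), discontinuation reasons (SAP 6.8.4) and AEs leading to interruption or withdrawal (SAP 6.9.1) would all show the hold. A treatment-related delay of 4 weeks or more in the next cycle is also a DLT criterion (Protocol 4.3.3).
- *AE rates are distorted.* SAP 6.9.1 reports AEs as numbers and percentages of participants; no exposure-adjusted rate is planned.

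The two-dose hold is the largest case described in Protocol 6.6.2. A participant who stops without a hold has no withheld doses to lose, and the documents give no frequency for either.

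**Conclusion.** Two separate points stand, both confined to descriptive exposure summaries.

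First, the stated DOT formula understates duration by 13 days per participant. This assumes that the last dose should carry its full 14-day interval. The gap shrinks if death or data cut-off falls within that interval. The change of category at seven doses rests on a cut of about 91 days.

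Second, the dose-intensity ratio is not fully pre-specified. For 2 doses given and 2 withheld before a permanent stop, it is 100%, 50% or 25% under three readings of the treatment period, and its unit label is wrong for its formula.

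No primary endpoint, escalation rule or AE rate uses either quantity. Protocol 4.3.6 does ask whether the MTD is feasible for long-term administration, and these summaries bear on that question, but it does not name dose intensity as a criterion. The wording should be corrected; the trial's main conclusions do not hang on it.

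**What to change.** In SAP 6.8.5:

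1. Define DOT as last dose date − first dose date + 14, capped at death or data cut-off, and give the day count used for the 3-month categories.
2. For dose intensity, define the treatment period as running from first dose to the decision to discontinue permanently, or data cut-off. Count every planned dosing day in it, including 0 mg days. State that planned days continue every 14 days through a hold, because Protocol 6.6.2 restarts the cycle count when treatment resumes after Day 28.
3. Do not use the end-of-treatment visit date as the end of the period. Protocol 1.3.2 allows that visit up to 28 days after the last dose, so a participant who stops for progression could be charged with doses that nobody meant to give.
4. Relabel the unit from mg/day to mg per scheduled dose.

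The first two changes need separate wording, since neither achieves the other. The cost is a few lines of SAP text and two derivations, with no change to trial conduct. Protocol 6.4 already has dose dates recorded on the CRF. The CRF itself is not among the documents, so the sponsor should confirm that the date of the decision to discontinue is captured. The downside is that dose intensity becomes slightly less favourable.
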